7.2 Subject-assessed duration of pain

Each subject will evaluate their pain daily on a visual analog scale contained in their diary card. They will begin their pain rating on Day 1 and end at their EOS visit.

8. SAFETY EVALUATIONS

8.1 Adverse Events

8.1.1 Treatment Emergent Adverse Events

An adverse event (AE) or adverse experience is any untoward medical occurrence in a individual who is using the study product and that does not necessarily have a causal relationship with the study product but that occurs after the start of dosing and up to 2 days after the EOS visit. An AE can therefore be any unfavorable and unintended sign, symptom, or disease temporally associated with the use of the study product, whether or not considered related to it. Pre-existing conditions, which increase in frequency or severity or worsen in nature during or as a consequence of use of a drug in human clinical studies, will also be considered as adverse experiences.

An AE **does not** include:

- Medical or surgical procedures (e.g., surgery, endoscopy, tooth extraction, transfusion). The condition that leads to the procedure is the AE.
- Situations where an untoward medical occurrence has not occurred (e.g., hospitalization for elective surgery, social and/or convenience admissions).
- Worsening of symptoms associated with expected progression of periodontal disease are not considered an adverse event in this study

8.1.2 Evaluation and Reporting of Adverse Events

All AEs (i.e. a new event or an exacerbation of a pre-existing condition) that occur after the start of dosing and up to 2 after the EOS visit, will be recorded as an AE or SAE (if applicable). (Any event occurring prior to start of treatment on Day 1 will be recorded as part of the subject's medical history.) All subjects who have used the study product at least once will be evaluated for safety.

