6.1.2 Induction Visit

Upon reporting to the clinic for their induction visit, the subject will be randomized to receive either EED or Abreva. The following assessments will then be performed to establish baseline values prior to dosing:

- Review of Medical History and Concomitant Medications for any changes between Screening and Day 1 (Treatment emergent AEs are collected in this study beginning with first instance of dosing. Any unusual symptoms prior to the start of dosing will be recorded, if appropriate, as an update to the subject's medical history).

- Limited Physical Exam to check for any changes between Screening and Day 1(changes in PE after start of dosing will be assessed as possible treatment emergent AEs)

If the subject remains qualified for the study:

- They will be dispensed study product (EED or Abreva) and instructed to use it 5 times daily beginning when they first sense a prodrome or see a lesion (they will be asked to note the day and time of their first dose on their diary card).
- They will be given a diary card and instructed how to complete it. A practice diary completion may be done to ensure that subjects know how to complete the diary.

Subjects will then be discharged from the clinic with an appointment to return on Day 3 via virtual video call. They will be instructed to bring their Diary Card and the tube/bottle of study product that they have received.

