8.1.3 Serious Adverse Events

An SAE is an AE from this study that results in any of the following outcomes:

- Death
- Life-threatening situation (subject is at immediate risk of death)
- Inpatient hospitalization or prolongation of existing hospitalization

- Persistent or significant disability/incapacity
- Congenital anomaly/birth defect in the offspring of a subject who received study dentifrice
- Considered significant by the investigator for any other reason

Important medical events that may not result in death, be immediately life-threatening, or require hospitalization, may be considered an SAE when, based upon appropriate medical judgment, they may jeopardize the subject or may require medical or surgical intervention to prevent one of the outcomes listed in this definition.

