8.1.4 Serious Adverse Event Reporting Requirements

- Within 24 hours of the Investigator's knowledge of an SAE, the site should contact the manufacturer (Livionex) and report the circumstances of the SAE.
- This initial reporting should contain as much information as is available to the Investigator.
- The Investigator should also notify the IRB of Serious Adverse Events occurring at the site in accordance with local procedures.

The Investigator must take all therapeutic measures necessary for resolution of the SAE. Any medications necessary for treatment of the SAE must be recorded onto the concomitant medication section of the subject's CRF.

The blind may not be broken unless it is determined necessary in order to provide appropriate treatment to the subject. Upon breaking of the blind or the final unblinding of study data, if the event is related to Abreva, the Investigator will notify Avinir Pharmaceuticals of the SAE.

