9.3 Safety Analysis

The safety analysis will be conducted on the Safety population.

Collection of AEs will begin on the first day of treatment and will be reported in simple per-subject listings.

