10. SCHEDULE OF ASSESSMENTS

ASSESSMENT	SCREENING	Induction Visit	Daily after induction visit to Day 1	DAY 1	DAY 5	DAY 7	DAY 10/ EOS	Follow -up phone call (EOS +2 days)
Informed Consent	X							
Medical/HSV History	X	X (med hx only)						
Urine Pregnancy Test (for woman of child bearing potential only)	X							
Limited Physical Exam	X	X						
Concomitant Medications	X	X						X
UV susceptibility test / MED testing	X (exposure)							
MED Reading		X						
Randomization		X						
UV exposure at 3 x MED (cold sore inducing)		X						
Study Product Dispensed		X						
Dosing Begins				X				
Dosing Ends						X		
Collect Study Product (including empty tubes/bottles)							X	
Photograph of irradiated area and lesion may be taken		X		X	X	X	X	X
Measurement of lesion (if possible)				X	X	X	X	X
Dispensing of Diary Card		X						
Review of Diary Card/Dosing compliance				X	X	X	X	
Solicitation of Adverse Events			X	X	X	X	X	X
Rating of lesion by blinded assessor				X	X	X	X	
Phone call to check for prodromal senses			X

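### The text starts adverse events at first dose while the schedule solicits them from induction; as written, a serious pre-dose UV reaction has no SAE route, and undosed induction failures fall outside the safety population and the independent review

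*Combined protocol and SAP*

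**What the plan says.** Four places in the protocol tie adverse events to dosing:

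- Section 8.1.1 defines an AE as an occurrence in someone using the product that "occurs after the start of dosing and up to 2 days after the EOS visit".
- Section 8.1.2 adds that "Any event occurring prior to start of treatment on Day 1 will be recorded as part of" the medical history. It makes no exception for serious events.
- Section 6.1.2 says the same more loosely: "Any unusual symptoms prior to the start of dosing will be recorded, if appropriate, as an update to the" medical history.
- Section 9.3 states that "Collection of AEs will begin on the first day of treatment" and reports AEs as per-subject listings.

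The schedule in section 10 reads differently. Its row "Solicitation of Adverse Events" is marked in the column for the daily contacts between the Induction Visit and Day 1, which is before dosing. It has no mark at Screening or Induction.

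Seriousness depends on the AE definition: "An SAE is an AE from this study that results in any of the following outcomes" (section 8.1.3). Section 8.1.4 then sets a 24-hour report to the manufacturer and says that "The Investigator should also notify the IRB of Serious Adverse Events occurring at the site in accordance with local procedures".

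Section 3 places the lip exposure at 3 times MED at the Induction Visit. Dosing begins at the prodrome, and a subject with no prodrome within 7 days is an induction failure. The synopsis (Treatment Period) discharges such subjects. Section 9.1 bases the Safety population on product use, and section 8.2 bases the independent review on subjects who have reached EOS.

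**The concern.** Starting product treatment-emergent AEs at first dose is ordinary practice. The difficulty is that this trial also imposes a procedure, UV irradiation, that can itself cause harm and that always precedes the product. No AE or SAE category covers harm from it before dosing. An entry in the medical history carries no seriousness assessment, has no route into section 8.1.4 and does not appear in the section 9.3 listings. For an induction failure, the text gives no path from such an entry to the independent reviewer. Staff also receive two instructions: the schedule tells them to solicit adverse events on the daily calls, while the text says that AE collection has not yet begun. What is at stake is the protection of irradiated subjects and complete safety reporting, not the efficacy result.

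**Working it through.** The plan states no figure to reproduce on this point. The check traces the definitions and then bounds the number of subjects affected.

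**Step 1: timing.** Lip exposure takes place at the Induction Visit, and first dose is at the prodrome (section 3). The longest interval before a subject is declared an induction failure is 7 days. Every dosed subject passes through the interval between exposure and first dose, and an induction failure never leaves it.

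**Step 2: a serious reaction within that interval.**

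| Question | Governing text | Result |
|---|---|---|
| Is it an AE? | 8.1.1, 8.1.2, 9.3 | No; it precedes dosing and becomes medical history |
| Is it an SAE? | 8.1.3 | No; an SAE must be an AE |
| Does it trigger 8.1.4? | 8.1.4 | Not by its terms; both the manufacturer report and the IRB bullet are written for SAEs |
| Is it solicited? | Section 10 | Yes, daily from induction to Day 1 |

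The last row conflicts with the first. No passage turns the solicited report into an AE.

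**Step 3: induction failures.** They have no prodrome, so under the plan they take no dose and return the product (section 3). They are then discharged. Section 9.1 requires product use, so they are not in the Safety population. Section 8.2 requires EOS to have been reached, and no EOS visit is described for them. Weekly follow-up to resolution (section 3) is written only for AEs still open at EOS.

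**Step 4: how many subjects.** Inputs from section 3: at most 35 consented and 20 completers.

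- Upper bound on irradiated, undosed subjects: 35 − 20 = 15, which is 15/35 = 43% of those irradiated.
- Lower bound: 0.

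The upper bound assumes that 35 consent, 20 complete, and all of the other 15 are induction failures. Each of those 15 who fails screening, or who is dosed but does not count among the 20, lowers it. The documents do not give the split.

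**The case against.** The strongest reply is that much of this is already covered.

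- The schedule solicits adverse events daily after induction, so reactions would probably be heard of.
- Section 3 sends unusual symptoms to medical personnel even before treatment.
- Section 6.1.2 includes a history review and a limited physical examination at induction.
- Section 6.2 asks for the EOS assessments when a subject wants to stop at any time, which would include someone who withdraws over a UV reaction.
- Section 8.1.1 counts as adverse experiences "Pre-existing conditions, which increase in frequency or severity or worsen in nature during or as a consequence of use of a drug", so a reaction that worsens under product use is captured.
- Section 6.3 adds calls after the final study visit.
- Local IRB procedures and the Study Manual cited in section 6.1.1 may hold a further route; neither is visible here.

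All of this stands as partial coverage. It rules out a stronger reading that a reader might infer, namely that pre-dose UV reactions would go unnoticed or that a serious one would reach nobody. The documents do not support that reading.

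What the coverage does not do is change the classification. The stated outcome in section 3 before treatment is a possible update of the medical history. The worsening clause does not help when a reaction peaks before dosing, or when the subject is never dosed. Section 6.2 does not mention routine induction failures. A call under section 6.3 to an undosed subject still cannot yield an AE under section 8.1.1. The important-medical-event wording in section 8.1.3 is discretionary and sits within a definition that requires an AE.

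A fair practical objection is that recording everything from the first exposure could make the intended erythema an AE in every subject. The fix must therefore exclude it.

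**Conclusion.** The point holds as a conflict between the schedule and sections 6.1.2, 8.1.1, 8.1.2 and 9.3, with a consequence for reporting. For up to 7 days after the lip exposure, a serious UV reaction does not by the protocol's terms become an SAE. Irradiated, undosed induction failures are outside both the Safety population and the EOS-based review. They number 0 to 15 if 35 are consented and 20 complete, with the split unstated.

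A reader might also infer that the safety comparison between EED and the comparator is biased. It is not affected: both arms undergo the same UV procedure, and the comparison rightly concerns events from first dose. The conclusion is limited to the protocol's own terms, because local IRB procedures and the Study Manual cannot be seen. The change should be made, but no efficacy or between-arm conclusion depends on it.

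Three neighbouring inconsistencies are separate editorial matters and add no weight here: the minimum product use that defines the Safety population (section 9.1 against 8.1.2), the number of follow-up calls (section 6.3 against the synopsis and schedule), and the step of 10 per group of 5 in section 8.2.

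**What to change.** Reconcile the section 10 schedule with sections 6.1.2, 8.1.1, 8.1.2 and 9.3 as follows:

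1. Record AEs and SAEs from the first study UV exposure, each flagged as UV-procedure or study product.
2. Exclude the expected erythema at the exposed site unless it meets a seriousness criterion or exceeds what the investigator expects.
3. Keep product treatment-emergent AEs, from first dose, as the subset for the EED versus comparator listing.
4. Apply the seriousness assessment of section 8.1.3 and the notification of section 8.1.4 to UV-procedure events.
5. List irradiated, undosed subjects separately and give that listing to the independent reviewer.

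The cost is small but not zero: protocol wording, one flag on the AE form, a longer listing and a few follow-up contacts. The daily calls, the solicitation from induction to Day 1 and the return of product by induction failures are already planned.

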8.1.3 Serious Adverse Events

An SAE is an AE from this study that results in any of the following outcomes:

- Death
- Life-threatening situation (subject is at immediate risk of death)
- Inpatient hospitalization or prolongation of existing hospitalization

- Persistent or significant disability/incapacity
- Congenital anomaly/birth defect in the offspring of a subject who received study dentifrice
- Considered significant by the investigator for any other reason

Important medical events that may not result in death, be immediately life-threatening, or require hospitalization, may be considered an SAE when, based upon appropriate medical judgment, they may jeopardize the subject or may require medical or surgical intervention to prevent one of the outcomes listed in this definition.

8.1.4 Serious Adverse Event Reporting Requirements

- Within 24 hours of the Investigator's knowledge of an SAE, the site should contact the manufacturer (Livionex) and report the circumstances of the SAE.
- This initial reporting should contain as much information as is available to the Investigator.
- The Investigator should also notify the IRB of Serious Adverse Events occurring at the site in accordance with local procedures.

The Investigator must take all therapeutic measures necessary for resolution of the SAE. Any medications necessary for treatment of the SAE must be recorded onto the concomitant medication section of the subject's CRF.

The blind may not be broken unless it is determined necessary in order to provide appropriate treatment to the subject. Upon breaking of the blind or the final unblinding of study data, if the event is related to Abreva, the Investigator will notify Avinir Pharmaceuticals of the SAE.

8.2 Independent Safety Review

An independent clinician will be assigned to review all available safety assessments on subjects as soon as 5 subjects reach EOS. This reviewer will be blinded to study treatment unless a safety concern is raised that requires identification of the subject's treatment group. Each subsequent safety evaluation will be conducted as 5 more subjects reach EOS and will include all available information from all subjects that have reached at least EOS. In other words, with each group of 5 subjects, the total reviewed will increase by 10 until all 20 subjects are included in the final independent safety evaluation.

The independent clinician will advise the Principal Investigator of any safety concerns or trends that could be a reason to terminate a specific subject's participation or to stop the study until it is deemed safe to continue.

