	
study medication and instructed how to apply it to the exposed area. When the patient first senses the start of developing a cold sore and applies study medication will be considered Day 1. Dosing of the study product will be done five times daily, beginning at the time that a subject first senses the start of the prodromal phase (Day 1). Subjects will be given a diary card to record their pain levels, progression of lesion development and any unusual symptoms (not normally seen with their outbreaks).
 
Patients will be called daily by the study team after their induction visit to determine the start of prodrome. If after 7 days, the patient does not develop any prodromal senses, the patient will be considered an induction failure.
 
When the patient first senses signs or symptoms of a cold sore, they will have the Day 1 visit conducted within 24 hours. Day 1 visit may be conducted in person or as a MyChart Virtual Visit. Their diary card will be reviewed and if they have experienced a prodrome and/or lesion since the induction visit, their compliance with dosing will be checked. If the subject has noted any unusual symptoms, these will be discussed with medical personnel to determine if the symptoms represent a treatment emergent AE. A photo will be taken of the irradiated area (as marked at the induction visit). The blinded assessor will assess the prodrome and/or lesion and take measurements.
 
On Days 3, 5, and 7, the subject will return to the clinic or follow up via virtual video call for assessment of the irradiated area. Study staff will review the subject diary to determine if the subject is correctly noting the lesion stage. Subjects will have a photo taken of the radiated area and asked to continue with dosing as instructed. Any diary card notation of unusual symptoms in subjects will be reviewed by study staff to determine if the symptoms represent a treatment emergent adverse event. The blinded assessor will assess the prodrome and/or lesion and take measurements. More study product may be dispensed as needed. Most subjects' lesions will have resolved by day 7, and they will end study treatment after 7 full days of treatment. If lesion has not resolved by day 7, the maximum number of days the patient may use study drug treatment is 10 days.
 
The EOS is the final study visit will take place on Day 10. A photo will be taken of the irradiated area, the diary card will be carefully reviewed and study product (including empty containers) will be collected. If subjects reach EOS without full resolution of their lesion(s), they will be given the option to begin taking a prn medication for the remainder of the outbreak. Measurements will be taken. If an adverse event has occurred but has not resolved by the EOS visit, the subject will be contacted once weekly and status noted until such time as the event has resolved. The blinded assessor will assess the prodrome and/or lesion.
 
A Safety follow-up phone call will occur 2 days after the EOS to determine if any new AEs have occurred.
 
Safety will also be evaluated by an independent physician throughout the study. The first independent safety evaluation will be done once 5 subjects

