--	--

[figure not shown]
	have reached EOS. Thereafter, the independent safety evaluation will occur as each subsequent group of 5 subjects reaches EOS and will include data on all subjects having reached EOS.
Enrollment Period	Subjects will be enrolled over a 2 year period.
Treatment Period	Subjects will be treated for up to 7 days from the time they first experience a prodrome and/or a lesion. If lesion has not resolved by day 7, the maximum number of days the patient may use study drug treatment is 10 days. If subjects reach EOS without full resolution of their lesion(s), they will be given the option to begin taking a prn standard of care medication for the remainder of the outbreak. Subjects that do not exhibit a prodrome within 7 days of the induction visit, will be considered induction failures and be discharged from the study. Total time of study participation for any given subject may range from 13 to 25 days.
Location	University of Utah MidValley Clinic, Department of Dermatology
Safety Assessments	Solicited AEs by review of diary cards and discussion with subjects
Efficacy Assessments	Primary: 
Number of subjects that experience prodrome (Stage 1) but do not progress to vesicles (Stage 3) by completion of treatment Secondary: 
Subject-assessed duration of painClinician-assessed duration of lesion appearance (Stage 3), as reported by subject, to complete healing (Stage 5)Measurement of cumulative lesion area (all eruptions if more than 1)Measurement of each lesion (if more than one) from eruption (Stage 3) through healing of hard crust (Stage 4) to identify the largest lesion

TABLE OF CONTENTS

PROTOCOL SYNOPSIS	ERROR! BOOKMARK NOT DEFINED.
1. INRODUCTION	1
1.1 Background and Rationale	1
2. OBJECTIVE	2
2.1 Efficacy Endpoints	2
2.1.1 Primary:	2
2.1.2 Secondary:	2
2.2 Safety Endpoint	2
3. STUDY DESIGN	2
4. STUDY TREATMENT	4
4.1 EDTA Eye Drops	Error! Bookmark not defined.
4.2 Comparator: Abreva®	4
4.3 Randomization Codes	4
5. SUBJECT POPULATION	4
5.1 Inclusion Criteria	4
5.2 Exclusion Criteria	5
6. STUDY PROCEDURES	6
6.1 Study Visits	6
6.1.1 Screening Visit (Days -14 to 0)	6
6.1.2 Study Day 1 Visit (Baseline)	Error! Bookmark not defined.
6.1.3 Study Days 3 and 5 Visits	8
6.1.4 Study Day 7 +/- 1 day Visit	8
6.2 Study Day 10 Visit	Error! Bookmark not defined.
6.2.1 End of Study (EOS) Visit	Error! Bookmark not defined.
6.3 Early Discontinuation Visit	9
7. EFFICACY EVALUATIONS	9

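### SAE notices do not go to the independent clinician, whose safety review starts only at each 5 subjects reaching EOS

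*Combined protocol and SAP*

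**What the plan says.** Section 8.2 gives the schedule: "An independent clinician will be assigned to review all available safety assessments on subjects as soon as 5 subjects reach EOS". Further reviews follow as 5 more subjects reach EOS, "until all 20 subjects are included in the final independent safety evaluation". The reviewer is blinded unless a safety concern calls for the treatment group to be identified. The advice goes to the principal investigator and covers reasons to end a particular subject's participation "or to stop the study until it is deemed safe to continue".

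The synopsis (Design) opens more broadly: "Safety will also be evaluated by an independent physician throughout the study". The next sentences place the first evaluation at 5 subjects, after which "the independent safety evaluation will occur as each subsequent group of 5 subjects reaches EOS".

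Section 8.1.4 lists who hears of an SAE. Within 24 hours of the investigator's knowledge, "the site should contact the manufacturer (Livionex) and report the circumstances of the SAE". It adds: "The Investigator should also notify the IRB of Serious Adverse Events occurring at the site in accordance with local procedures". The maker of Abreva is told of events related to Abreva once the blind is broken. The independent clinician is not on the list.

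**The concern.** Advice to stop a study protects subjects only if it comes before more of them are exposed. Here each new subject is deliberately irradiated on the lip at 3 times the MED (section 3) and then given study product. The clinician in 8.2 is the only safety reviewer whom the plan makes both independent and blinded: section 3 leaves the principal investigator unblinded, and the manufacturer supplies the test product (4.1). As written, that reviewer need not hear of a serious event until the next group of 5 is complete. Later reviews are defined on subjects who have reached EOS, when product is collected and the subject is released (6.1.5), so advice about that particular subject would come after treatment had ended.

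**Working it through.** **Inputs.** Review at each 5 EOS (8.2; synopsis, Design). Target of 20 (sections 3 and 5), taken as the 20 reaching EOS, as 8.2 does. Accrual: "Subjects will be enrolled over a 2 year period" (synopsis, Enrollment Period). EOS at healing or Day 10, whichever is first (section 3). AE window from first dose to 2 days after EOS (8.1.1).

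**The plan's own count.** Groups of 5 put the reviews at 5, 10, 15 and 20. Section 8.2 also says that the total grows by 10 each time; that gives 5, 15, 25 and never reaches 20. This slip is separate and does not affect the point, because the trigger of 5 is stated in both 8.2 and the synopsis.

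**Count from the affected subject's own EOS.** For the k-th subject to reach EOS, with the event known by then, further completers up to and including the one who triggers the review = 5 × ceil(k/5) − k.

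- Positions 1, 2, 3, 4, 5 in a group: 4, 3, 2, 1, 0.
- Mean: (4 + 3 + 2 + 1 + 0)/5 = 2.
- Subjects 16 to 20: the next review is the one at 20, the final one.

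**Time, assuming even accrual of 20 completers over 2 years.** Spacing = 730/20 = 36.5 days. Longest wait = 4 × 36.5 = 146 days (4.8 months); mean = 2 × 36.5 = 73 days (2.4 months). An event on Day 1 with EOS on Day 10 adds 9 days.

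**Where the count exceeds 4.**

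- Overlap. Suppose the event starts when 9 subjects have reached EOS and another subject becomes the 10th. The second review is held on completers, without the affected subject, who then becomes the 11th. The next review is at 15, so subjects 10, 12, 13, 14 and 15 make 5. A simulation (20 starts uniform over the accrual period, EOS 5 to 10 days after Day 1, event at a random time on study) gave more than 4 in about 1.5% of cases with 2-year accrual and about 3% with 1-year accrual.
- An event in the 2 days after the EOS of the fifth subject of a group, once that review has been held, waits for the next group: 5 completers including the one who triggers it.
- A subject withdrawn after an SAE might not be counted as reaching EOS at all.
- Induction failures irradiated in the interval are in none of these counts.

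**With notice within 24 hours.** At the same average pace, about 1/36.5 = 0.03 further subjects would reach EOS before the clinician is told.

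The documents give no SAE rate, so no probability of such an event can be stated.

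**The case against.** The strongest reply is that little is lost. The clinician only advises. The investigator already knows of the event, the manufacturer hears within 24 hours, the IRB is notified, and nothing forbids calling the clinician at once. This stands, and it limits the weight of the point: a reader might infer that serious events go without oversight between reviews, and the documents do not support that. What is missing is a requirement to involve one reviewer.

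It can also be argued that the text implies an ad hoc role: safety is evaluated throughout the study, a safety concern may be raised, and advice may concern a single subject, which fits poorly with a role confined to completers. That is a fair reading of intent. But the synopsis goes straight on to the groups of 5, and neither place says who contacts the clinician, when, or about what.

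Two stronger readings should be resisted. A reader might take 4 as a ceiling; it is one only when counted from the affected subject's own EOS, with the event known by then. A reader might also infer that a prompt review would never delay enrolment, because irradiation to EOS takes at most about 7 + 10 = 17 days and 36.5 − 17 = 19.5 days then remain before the next completer is irradiated. But the next person irradiated need not be a completer. Up to 35 may be consented; if nearly all were irradiated at even intervals, spacing is 730/35 = 20.9 days and only 20.9 − 17 = 3.9 days remain. Clustered accrual would leave less.

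**Conclusion.** The gap is real and modest. Under the written rules the clinician assigned to advise on stopping need not learn of a serious event until 0 to 4 more subjects (mean 2) have reached EOS, counted from the affected subject's own EOS, and possibly more when counted from onset. In the last group the scheduled advice arrives with the final review, when little or nothing remains to stop. The counts rest on the cadence of 5 alone; the times rest on even accrual over 2 years. What is delayed is independent, blinded advice, not all oversight, and the effect is on subject safety only: no endpoint or analysis changes. Worth considering as a cheap improvement.

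**What to change.** In 8.1.4, add that the same 24-hour notice goes to the independent clinician, without the treatment assignment, for any event meeting the seriousness criteria of 8.1.3 from UV exposure onward. State that this includes events before the first dose. Otherwise these produce no notice, because 8.1.2 records them only as medical history, although the schedule in section 10 solicits adverse events daily after induction.

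In 8.2, add that on receiving a notice the clinician decides whether an unscheduled review is needed. Such a review covers all subjects irradiated or dosed so far, whether or not they have reached EOS, and the clinician may advise on subjects now on treatment and on holding further irradiation. Leaving the decision to the clinician is preferable to an automatic hold for related events: section 8.1 assigns nobody to judge relatedness, so the unblinded investigator would do so by default, and 8.1.3 counts as serious anything the investigator considers significant.

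The cost is two added rules in an amendment, using the clinician already assigned. The downside is an occasional extra review and possibly a short enrolment pause, which could force rescreening if it outlasts the 2-week screening window. How often this would happen cannot be estimated from the documents.
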